3.6.3.2 Neurological examination

Each neurological examination will include, but are not limited to:

- Cranial nerve examination: olfactory, optic, oculomotor, trochlear, trigeminal, abducens, facial, vestibulocochlear, glossopharyngeal, vagus, accessory, hypoglossal).
- Extrapiramidal features: postural tremor, rest tremor, intention tremor, cogwheel rigidity, lead pipe rigidity, bradykinesia, postural deficit, dystonia, other.
- Gait examination: antalgic, staggering, steppage, waddle, difficulty initiating, glue footed, toe walking, other.
- Coordination examination: finger to nose test, rapid alternating movements, heel to shin, tandem gait.
- Motor examination (tone): spasticity, rigidity, paratonia, other, decreased muscle tone.
- Peripheral nervous system (sensory disturbances).
- Reflexes examination.
- Strength examination: heel walking, sit to stand test, toe walking, other motor abnormality.

These examination findings will be assessed as normal or abnormal.

Number and percentage of participants with abnormal neurological examination will be summarized by location (cranial nerve, Extrapiramidal features, motor, Peripheral nervous system strength, reflex, sensory, coordination, gait) at each planned visit during the treatment emergent period.

3.6.3.3 *Ophthalmological examination*

The effect of venglustat on the lens will be closely monitored throughout the primary analysis period for all participants and throughout the whole study for participants <18 years of age. The full ophthalmological examination will include slit-lamp examination, fundoscopy with pupil dilation and examination of the cornea, lens, and retina.

So, the results will be presented for all participants in the first step analysis. In the second step, only participants in secondary population younger than 18 years will be included.

A full ophthalmological examination, photography, and ARLNS will be performed during screening (this will serve as a baseline assessment) and at Week 104 or at early withdrawal or treatment discontinuation for all participants.

If a lens abnormality is found, the ophthalmologist at the site should perform pupil dilation, photography, and ARLNS evaluation.

The full ophthalmological examination should be performed by the same ophthalmologist throughout the study, if possible. Abnormal findings reported by the clinical sites will be reviewed by the DMC and/or the clinical site to adjudicate these findings as an adverse event of special interest (AESI) and assess their seriousness/severity.

Secondary safety endpoints in first step, include change in the lens opacity by ophthalmological examination during the treatment emergent period.

Number and percentages of participants with abnormal ophthalmological examination on any eye at any time (whether present at screening or not) as well as number and percentages of participants with any new onset of abnormal ophthalmological examination on any eye during the treatment emergent period as per investigator (site ophthalmologist) assessment will be summarized along with a description of lens opacity according to the WHO classification.

The decrease in Best Corrected Visual Acuity (BCVA) will also be presented on any eye at any time (whether present at screening or not). This decrease will be presented according to 1, 2 or 3 lines.

3.6.3.4 *Depression [REDACTED] examination*

[figure not shown]
[REDACTED]

[REDACTED]

[REDACTED]

[REDACTED]

[REDACTED]

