Study Period/ Procedure	Screening	Primary analysis treatment period								Open-label extension treatment period				FU Period	Notes
Day or Week	Up to 60 d before D1	W1/D1	W12 (±7d)	W26 (±7d)	W39 (±7d)	W52 (±7d)	W65 (±7d)	W78 (±7d)	W104 (±7d)/EW ^a	W130 (±14d)	W156 (±14d)	W182 (±14d)	W208 (±14d)/EOT/EW ^b	W214 (±7d) SFU after EOT	
Visit number	1	2	3	4	4.1 ^c	5	5.1 ^c	6	7	8	9	10	11	12	
															phone visit or a remote monitoring may be required due to regional or national emergency as declared by a governmental agency.
Physical examination	X ^h	X ^h	X ^h	X ^h		X ^h		X ^h	X ^h	X ^h	X ^h	X ^h	X ^h	X ⁱ	^h complete/full physical examination including visual acuity. ⁱ abbreviated/brief physical examination.
Neurological examination	X								X		X		X		When neurological and ophthalmological examinations are performed on the same day, the neurological examination should be performed before the ophthalmological examination.
Body weight	X	X	X	X		X		X	X	X	X	X	X	X	
Height	X	X ^j	X ^j	X ^j		X ^j		X ^j	X ^j	X ^j	X ^j	X ^j	X ^j		^j For juvenile and adolescent participants only.
Archival blood sample		X													This sample will be collected and stored for use if any unexpected safety issue occurs to ensure that a predose baseline value is available for previously nonassessed parameters.
Vital signs	X	X	X	X		X		X	X	X	X	X	X	X	Includes heart rate, systolic and diastolic blood pressure, respiratory rate, and body temperature.
Serum β-hCG	X														

Study Period/ Procedure	Screening	Primary analysis treatment period								Open-label extension treatment period				FU Period	Notes
Day or Week	Up to 60 d before D1	W1/D1	W12 (±7d)	W26 (±7d)	W39 (±7d)	W52 (±7d)	W65 (±7d)	W78 (±7d)	W104 (±7d)/EW ^a	W130 (±14d)	W156 (±14d)	W182 (±14d)	W208 (±14d)/EOT/EW ^b	W214 (±7d) SFU after EOT	
Visit number	1	2	3	4	4.1 ^c	5	5.1 ^c	6	7	8	9	10	11	12	For further details, see footnote "c" at the end of the table.
pregnancy test (for WOCBP)															
Urine pregnancy test (for WOCBP)		←-----Every 4 weeks-----→												Female patients of childbearing potential only. Results will be captured in patient diary when test is not taken at the clinic. At V2, it must be negative before the first IMP administration.	
Serology tests for hepatitis B, C, and other infectious disease, if locally required	X														

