
Primary population:
 
 To assess the PD of daily oral dosing of venglustat and the effect of venglustat on selected performance test and scale over a 104-week period. 	
 Absolute change in CSF GM2 biomarker from baseline to Week 104. Change in 25-foot walk test (25FWT) from baseline to Week 104 (in participants able to walk at baseline). Change in the neurological examination of the Friedreich's Ataxia Rating Scale (FARS) from baseline to Week 104. 												

Primary population:
 
 To determine the safety and tolerability of venglustat when administered orally once daily over a 104-week period. 	
 Changes from baseline to Week 104 in the following: 
 Assessment of adverse events (AEs) and concomitant medication Neurological examination Ophthalmological examination Vital signs Clinical laboratory evaluations including hematology, biochemistry, urinalysis, and serology Electrocardiogram (ECG) 												

[figure not shown]
Objectives	Endpoints
Primary population: 
To assess the pharmacokinetics (PK) of venglustat in plasma and CSF.	
Plasma and CSF venglustat concentrations at prespecified visits over the study duration and plasma PK parameters (when applicable) including maximum plasma concentration observed (C_{max}), t_{max}, and area under the plasma concentration versus time curve calculated using the trapezoidal method over a predefined time period (from time t=0 to 24 hours; AUC_{0-24}).
Secondary population: 
To assess the effect of venglustat on selected performance tests and scale over a 104-week period.	
Annualized rate of change in the 9-HPT from baseline to Week 104.Change in 25FWT from baseline to Week 104 (in participants able to walk at baseline).Change in the neurological examination of the FARS from baseline to Week 104.

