5.2 EXCLUSION CRITERIA

Participants are excluded from the study if any of the following criteria apply:

Medical conditions

E 01. Participant has clinical features of Tay-Sachs or Sandhoff disease, but a completely negative result on a genetic test for GM2 gangliosidosis caused by β -hexosaminidase deficiency resulting from mutations in the [REDACTED] and/or is without clinical features.

- E 02. For primary population and participants with juvenile/adolescent late onset GM2 gangliosidosis and GM1 gangliosidosis, the participant cannot understand and perform all age-appropriate study assessments, with the exception of 25FWT and PROs.
- E 03. Any clinically relevant medical disorders other than late-onset GM2 gangliosidosis (primary population) or the diseases specified for the secondary population, clinically relevant findings in the physical examination, medical history, or laboratory assessments which would compromise the safety of the participant. This includes condition(s) that precludes the safe performance of routine lumbar puncture (eg, prohibitive lumbar spinal disease), as well as cardiovascular, renal, hepatic, gastrointestinal, pulmonary, neurologic, endocrine, metabolic (eg, hypokalemia, hypomagnesemia), or psychiatric disease, other medical conditions, or serious intercurrent illnesses.
- E 04. The participant has a documented diagnosis of any of the following infections: hepatitis B, hepatitis C, human immunodeficiency virus 1 or 2.
- E 05. A history of drug and/or alcohol abuse within the past year prior to the first screening visit.
- E 06. The participant is scheduled for in-patient hospitalization including elective surgery during the study.
- E 07. The participant has, according to World Health Organization (WHO) grading, a cortical cataract \geq one-quarter of the lens circumference (Grade cortical cataract-2) or a posterior subcapsular cataract ≥ 2 mm (Grade posterior subcapsular cataract-2). Participants with nuclear cataracts will not be excluded.

Prior/concomitant therapy

- E 08. The participant requires use of invasive ventilatory support.
- E 09. The participant is receiving current treatment with anticoagulants (eg, coumadin, heparin) that might preclude safe completion of the LP.
- E 10. The participant has received SRT within 3 months prior to study enrollment.

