3 STATISTICAL ANALYSES

3.1 GENERAL CONSIDERATIONS

Statistical significance for comparison between venglustat and placebo will be assessed at the Type I error rate of 0.05 one sided. Although a typical criterion for concluding that a trial is positive is a p-value of <0.05 two-sided, a higher Type I error rate of 0.05 one-sided was selected due to the rarity of late-onset GM2 gangliosidosis, the seriousness of this disease and lack of available therapy, as per Food and Drug Administration (FDA) draft guidance (1).

In general, continuous data will be summarized using the number of observations available, mean, standard deviation (SD), median, [Q1, Q3] minimum, and maximum. Categorical and ordinal data will be summarized using the count and percentage of participants.

The baseline value is defined as the last available value before or equal to the first dose of investigational medicinal product (IMP) date in the primary analysis period. For participants randomized but not exposed, the baseline value is defined as the last available value before or equal to the date of randomization.

Unless otherwise specified, analyses will be performed by intervention group (and overall for baseline and demographics characteristics).

The two analysis periods described below are defined:

- The **primary analysis period** is defined as the period starting at the date of signed informed consent, and ending at the end of Week 104 visit, or the day before the first IMP OLE administration (whichever comes last). For participants not exposed to IMP in the OLE, the primary analysis period ends at the date of end of study.
- The **OLE period** (only for participants exposed to IMP in the OLE) is defined as the period starting the day after the end of primary analysis period, until the end of the study.

Within each analysis period, the following observation periods are defined:

During the **primary analysis period** (as defined above), the following observation periods are defined:

- The **pre-treatment period** is defined as the time from the signed informed consent date up to the first IMP administration.
- The **treatment-emergent (TE) period** is defined as the time from the first IMP administration to the last administration of IMP during the primary analysis period +6 weeks (including any temporary treatment discontinuation period, if any) or the end of the primary analysis period (whichever comes first).

The TE period includes the following 2 periods:

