5.4 APPENDIX 4 DATA HANDLING CONVENTIONS

General conventions

The following formulas will be used for computation of parameters.

Demographic formulas

- $$\text{BMI} = \frac{\text{weight(kg)}}{\text{height(m)}^2}$$

Missing data for primary/secondary efficacy endpoints

The primary analysis will include all data collected in participants from the primary population, regardless of whether or not participants completed the treatment period. Participants who prematurely and permanently discontinue study medication will be requested to continue to be assessed after treatment discontinuation, up to the Week 104 visit. Data collected after treatment discontinuation will be included in the primary analysis. All efforts will be made to minimize the amount of missing data.

The linear mixed effect model described in [Section 3.2.2.2](#) will be run on all observed data, including data collected after treatment discontinuation. Missing data will be handled by the model assuming a Missing At Random mechanism.

Due to the small sample size in this study, it is expected that a model-based imputation of missing data will not be feasible. In particular, imputation of missing data based on a model estimated from participants from the same treatment arm who discontinued the study treatment but continued to have their data collected will likely be unfeasible, due to the small number of participants in this category.

Age for children/adolescents participants for derivation of PCSA

For children/adolescents participants, the PCSA definition depends on the category of age. Therefore, it is necessary to derive the age during the study. For this purpose, the age during the study will be defined as the age at screening plus the time (in years) since randomization.

Analysis windows for time points

For all analyses, D1 will be defined as the reference date of the participant. For treated participant, the reference date will be the day of first IMP intake. For the other participants, randomized but not treated the reference date will be the day of randomization.

For endpoints not collected at each visit (CSF biomarkers, neurological examination), analysis by time points will be summarized using the protocol planned visits.

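### The neurological-examination safety endpoint is change from baseline to Week 104, but the SAP tabulates only percent abnormal after dosing, which cannot show within-participant change

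*SAP*

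**What the plan says.** Protocol Section 3 (Table 3) and SAP Section 1.2 (Table 2) list the neurological examination, for both populations, under the heading "Changes from baseline to Week 104 in the following".

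The Protocol's Schedule of Activities (Section 1.3) places this examination at screening, Week 104 or early withdrawal, Week 156 and Week 208. There is thus one examination before treatment and one scheduled examination after dosing in the double-blind period.

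SAP 3.6.3.2 puts each finding on a two-level scale: "These examination findings will be assessed as normal or abnormal". The one summary planned is "Number and percentage of participants with abnormal neurological examination will be summarized by location", given "at each planned visit during the treatment emergent period". SAP 3.1 says that for the primary analysis period this window "is defined as the time from the first IMP administration to the last administration of IMP during the primary analysis period +6 weeks", or to the end of that period if sooner.

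SAP 5.4 adds only a visit rule: "For endpoints not collected at each visit (CSF biomarkers, neurological examination), analysis by time points will be summarized using the protocol planned visits". The examination is not among the baseline characteristics in SAP 5.3.

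Other safety data are tied to baseline. SAP 3.6.3.1 gives changes from baseline for laboratory, vital-sign and ECG variables and splits their abnormalities by baseline status. SAP 5.4 mentions shift summaries for the same three. SAP 3.6.3.3 counts new-onset abnormalities for the eye examination.

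**The concern.** The endpoint is a change, but the planned output is a cross-section after dosing. A participant abnormal at Week 104 may have been abnormal at screening or may have become so on treatment, and the table counts both alike. Someone who became normal and someone who became abnormal cancel out in the arm percentage.

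This matters more than usual here. The disease is neurological and progressive, and exclusion criterion E 01 removes anyone who "and/or is without clinical features", so some locations will be abnormal at entry in many participants. Venglustat crosses the blood-brain barrier, and Protocol 2.3.1.2 says neurological and psychiatric events are monitored for that reason. Followed as written, the SAP would leave a named safety endpoint unestimated although the data to estimate it are collected.

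**Working it through.** The documents state no figure for this endpoint, so there is none to reproduce. The check has two parts.

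**1. From endpoint to table**

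- Endpoint: change from baseline to Week 104 (Protocol Table 3, SAP Table 2).
- Baseline examination: screening only (Protocol 1.3).
- Window of the planned table: opens at first dose (SAP 3.1), so screening is outside it.
- Content of the planned table: number and percentage abnormal by location (SAP 3.6.3.2).
- Baseline comparison, shift or new-onset count: not found for this examination in SAP 3.6.3.2, 5.3 or 5.4.

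The table holds only the Week 104 margin. Within-participant change needs the joint distribution of screening and Week 104 results, which a margin does not give.

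**2. Size, over assumed baseline rates**

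Inputs: 38 venglustat and 19 placebo participants (SAP Section 4). The proportion *b* abnormal at entry in a location is not in the documents, so a range from 30% to 95% is assumed. For illustration, 25% of venglustat participants normal at entry become abnormal, and none do on placebo.

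- Standard error of the between-arm difference: SE = sqrt[b(1−b)(1/38 + 1/19)]. At b = 0.30, sqrt(0.21 × 0.0789) = 0.129.
- Venglustat participants normal at entry: 38(1−b).
- Newly abnormal: 0.25 × 38(1−b).
- Rise in the venglustat percentage: 0.25(1−b).

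| Abnormal at entry (assumed) | SE of difference, points | Rise in % abnormal, points | Normal at entry, venglustat | Newly abnormal |
|---|---|---|---|---|
| 30% | 12.9 | 17.5 | 26.6 | 6.65 |
| 50% | 14.0 | 12.5 | 19.0 | 4.75 |
| 80% | 11.2 | 5.0 | 7.6 | 1.90 |
| 90% | 8.4 | 2.5 | 3.8 | 0.95 |
| 95% | 6.1 | 1.25 | 1.9 | 0.48 |

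At 80% abnormal at entry, the planned table would move from 80% to 85%, a rise of less than half the standard error. A shift table would show the same events directly, as about 2 new abnormalities among about 8 participants normal at screening. At 30%, the rise exceeds the standard error, so the planned table keeps some between-arm information. At 95%, fewer than 2 venglustat participants are at risk, and neither table can show much new onset. A binary result cannot show worsening within a location already abnormal, at any baseline rate.

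**The case against.** - **The table is by location and by randomized arm.** Protocol 2.2.1 describes chronic phenotypes dominated by different parts of the CNS, so some locations may be mostly normal at entry. Chance imbalance at entry adds noise to a randomized comparison, not bias. This stands. It limits the point to missing within-participant change and to the ceiling where abnormality is common.

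- **Neurological change is covered elsewhere.** FARS-neuro is a graded 0 to 117 score measured repeatedly and compared for change by arm (SAP 3.3.1.2.3). Protocol 8.2.1 asks for new or worse physical-examination findings to be reported as adverse events. This stands in part. FARS-neuro is a different instrument analyzed as efficacy, and Protocol Appendix 3 does not count expected progression of the studied disease as an adverse event unless it is more severe than expected. Neither analyzes this endpoint.

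- **The endpoint heading is generic.** It also covers adverse events and concomitant medication, for which change is a loose term. That is so, but a normal/abnormal finding with a screening value has a well-defined change.

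- **The omission of screening may be loose wording.** SAP 5.4 refers to protocol-planned visits, and screening is one. Even then, screening and Week 104 percentages side by side would be two margins without the link between them.

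- **The eye is a special case.** Lens opacity is an adverse event of special interest and the neurological examination is not. That could explain closer attention to the eye, but not why laboratory, vital-sign and ECG data are also tied to baseline.

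A reader might infer that the planned table is uninformative, that nearly everyone is abnormal at entry in gait, motor, coordination and strength, or that the plan as a whole cannot reveal a new neurological abnormality. The documents support none of these. E 01 requires clinical features but gives no rate by location, and FARS-neuro and adverse-event reporting remain. A reader might also rest the point on depression and syncope, for which Protocol Table 2 lists neurological examinations as mitigation. A normal/abnormal gait or cranial-nerve result measures neither well, so the point does not depend on it.

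**Conclusion.** The mismatch holds. The endpoint is change from baseline to Week 104. The only planned summary omits the baseline examination and carries no information on within-participant change. This follows from the text and needs no assumption.

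The size does rest on assumption, because no baseline rates are given. With arms of 38 and 19, the standard error of the between-arm difference is about 13 percentage points at 30% abnormal, peaks at 14 at 50% and falls to about 6 at 95%. Where abnormality at entry is common, new onset in a quarter of those at risk moves the planned percentage by 5 points or less.

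The consequence is limited to descriptive safety reporting. SAP 3.6 plans no safety testing, and the co-primary endpoints, the type I error and trial conduct are unaffected. It is still worth correcting, because the table as specified does not estimate the endpoint it serves.

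**What to change.** In SAP 3.6.3.2:

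1. Present the screening result by location and arm.
2. Add a shift table by location and arm from screening to Week 104 or early withdrawal: normal or abnormal at screening against normal or abnormal afterwards.
3. Give the number and percentage newly abnormal among those normal at screening, with the denominator shown. Keep it descriptive, in line with the new-onset count for the eye in 3.6.3.3.
4. State that a normal/abnormal shift does not capture worsening of an abnormality already present.
5. If the table is extended to Weeks 156 and 208 in the second-step analysis, present delayed and early venglustat separately. Use the last examination before first venglustat dose as the reference: screening for the early group and Week 104 for the delayed group. A shift from screening in the delayed group would include two years on placebo.

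The cost is a short SAP edit and one revised table. All the examinations are already scheduled, so no new data are needed.

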Hematology, biochemistry, urinalysis	X	X	X	X		X		X	X	X	X	X	X	X	Urinalysis by dipstick will be performed at the site. If abnormal, a complete urinalysis will be performed by the central laboratory
Urine biochemistry (including UPCR and UACR) ^k		X	X	X		X		X	X	X	X	X	X		

Study Period/ Procedure	Screening	Primary analysis treatment period								Open-label extension treatment period				FU Period	Notes
Day or Week	Up to 60 d before D1	W1/D1	W12 (±7d)	W26 (±7d)	W39 (±7d)	W52 (±7d)	W65 (±7d)	W78 (±7d)	W104 (±7d)/EW ^a	W130 (±14d)	W156 (±14d)	W182 (±14d)	W208 (±14d)/EOT/EW ^b	W214 (±7d) SFU after EOT	
Visit number	1	2	3	4	4.1 ^c	5	5.1 ^c	6	7	8	9	10	11	12	For further details, see footnote “c” at the end of the table.
															^k First morning void urine sample to be collected on the day of the site visit or home visit (where allowed per local regulations). Second morning void urine sample can be collected if first morning void urine sample was not collected. Courier transportation can be arranged as required and if allowed per local regulations. Urine sample should be sent to the central laboratory for quantitative measurement of creatinine, total protein and albumin which will be used to calculate the urine albumin/creatinine ratio and urine protein/creatinine ratio.
12-lead ECG	X	X ^l		X		X		X	X		X		X		^l ECG in triplicate will be performed prior to IMP administration. Please note that ECG is required in triplicate only at Visit 2.
Ophthalmological examination	X ^m			X ⁿ		X ⁿ		X ⁿ	X ^m	X ^o	X ^o	X ^o	X ^m		^m Full ophthalmological examination (including slit lamp fundoscopy with dilation), photography, and ARLNS for all participants.

Study Period/ Procedure	Screening	Primary analysis treatment period								Open-label extension treatment period				FU Period	Notes
Day or Week	Up to 60 d before D1	W1/D1	W12 (±7d)	W26 (±7d)	W39 (±7d)	W52 (±7d)	W65 (±7d)	W78 (±7d)	W104 (±7d)/EW ^a	W130 (±14d)	W156 (±14d)	W182 (±14d)	W208 (±14d)/EOT/EW ^b	W214 (±7d) SFU after EOT	
Visit number	1	2	3	4	4.1 ^c	5	5.1 ^c	6	7	8	9	10	11	12	For further details, see footnote "c" at the end of the table.

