															
n Full ophthalmological examination (including slit lamp funduscopy with dilation) for all participants.
 
o Full ophthalmological examination (including slit lamp funduscopy with dilation), for participants ≥2 and <18 years of age only.
 
Full ophthalmological examination, photography, and ARLNS can be performed at any time if deemed medically necessary. When neurological and ophthalmological examinations are performed on the same day, the neurological examination should be performed before the ophthalmological examination.

AE collection	X	X	X	X		X		X	X	X	X	X	X	X	AEs will be captured from the time the participant provides signed informed consent through the safety follow-up period up to 6 weeks after the W208 EOT visit.
Prior and concomitant medications	X	X	X	X		X		X	X	X	X	X	X	X	

Study Period/ Procedure	Screening	Primary analysis treatment period								Open-label extension treatment period				FU Period	Notes
Day or Week	Up to 60 d before D1	W1/D1	W12 (±7d)	W26 (±7d)	W39 (±7d)	W52 (±7d)	W65 (±7d)	W78 (±7d)	W104 (±7d)/ EW ^a	W130 (±14d)	W156 (±14d)	W182 (±14d)	W208 (±14d)/ EOT/EW ^b	W214 (±7d) SFU after EOT	W1/D1 visit will be Baseline visit. For further details, see footnotes “a” and “b” at end of the table.
Visit number	1	2	3	4	4.1 ^c	5	5.1 ^c	6	7	8	9	10	11	12	For further details, see footnote
Pharmacokinetics															
Plasma samples		X ^r	X ^s	X ^t		X ^t			X ^u						^r For primary population, sampling will be performed predose and 0.5, 3, 8, 12, and 24 hours postdose in 15 participants (Plasma sample ID P00, P01, P02, P03, P04, P05, respectively). This PK profile sub study will stop when required numbers of samplings are collected. For all other participants, sampling will be performed only at 3 hours postdose (P02). Participants will receive IMP at clinical site on this day.

Study Period/ Procedure	Screening	Primary analysis treatment period								Open-label extension treatment period				FU Period	Notes
Day or Week	Up to 60 d before D1	W1/D1	W12 (±7d)	W26 (±7d)	W39 (±7d)	W52 (±7d)	W65 (±7d)	W78 (±7d)	W104 (±7d)/EW ^a	W130 (±14d)	W156 (±14d)	W182 (±14d)	W208 (±14d)/EOT/EW ^b	W214 (±7d) SFU after EOT	
Visit number	1	2	3	4	4.1 ^c	5	5.1 ^c	6	7	8	9	10	11	12	For further details, see footnote "c" at the end of the table.

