8.2.5 Ophthalmological examination

The effect of venglustat on the lens will be closely monitored throughout the whole study for all participants. The full ophthalmological examination will include slit-lamp examination, funduscopy with pupil dilation and examination of the cornea, lens, and retina.

The evaluation of the lens by photography according to the Age-Related Eye Disease Study (AREDS) Clinical Lens Grading System (ARLNS) will be performed during screening, Week 104, Week 208, early withdrawal or treatment discontinuation, or any time deemed medically necessary.

A conventional confrontation visual field examination such as the Donders' test can be performed by the local ophthalmologist as needed as a part of the eye examination. Systematic visual field test by perimetry is not required for this trial.

A full ophthalmological examination, photography, and ARLNS will be performed during screening (this will serve as a baseline assessment), at Week 104 and at Week 208, or at early withdrawal or treatment discontinuation for all participants.

A full ophthalmological examination will be performed at Week 26, Week 52, and Week 78 for all participants and also at Week 130, Week 156, and Week 182 for participants aged ≥ 2 and < 18 years.

Full ophthalmological examination can be performed at any time if deemed medically necessary.

If a lens abnormality is found, the ophthalmologist at the site should perform pupil dilation, photography, and ARLNS evaluation.

The full ophthalmological examination should be performed by the same ophthalmologist throughout the study, if possible. Abnormal findings reported by the clinical sites will be reviewed by the DMC and/or the clinical site to adjudicate these findings as an adverse event of special interest (AESI) and assess their seriousness/severity.

When neurological and ophthalmological examinations are performed on the same day, the neurological examination should be performed before the ophthalmological examination.

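### SAP 3.6.3.3 leaves adult eye-examination results from the open-label extension, including Week 208, out of both analysis steps

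*SAP*

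**What the plan says.** **Protocol.** Section 8.2.5 sets the scope of lens monitoring: "The effect of venglustat on the lens will be closely monitored throughout the whole study for all participants". It places the full examination, with photography and lens grading, at screening and then "at Week 104 and at Week 208, or at early withdrawal or treatment discontinuation for all participants". In the Schedule of Activities (1.3), note m, marked at screening, Week 104 and Week 208, covers full examination, "photography, and ARLNS for all participants". The three examinations between Weeks 104 and 208 carry note o: "Full ophthalmological examination (including slit lamp funduscopy with dilation), for participants ≥2 and <18 years of age only". Section 8.2.5 also allows unscheduled examinations: "Full ophthalmological examination can be performed at any time if deemed medically necessary".

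**SAP.** Section 3.6.3.3 describes the scope differently. Lens monitoring runs "throughout the primary analysis period for all participants and throughout the whole study for participants <18 years of age". Its list of examinations goes from screening to the end of the primary period, "and at Week 104 or at early withdrawal or treatment discontinuation for all participants", and does not mention Week 208. First-step results cover all participants. For the second step the rule is: "In the second step, only participants in secondary population younger than 18 years will be included". The outputs planned in that section are participant counts of abnormal and new-onset findings, a description of lens opacity by WHO class, and loss of best corrected visual acuity (BCVA) by 1, 2 or 3 lines. SAP 3.8.2 confines the first step to data up to Week 104 and excludes everything collected in the OLE.

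**The concern.** The protocol collects an end-of-treatment eye examination from every adult who stays in the OLE, and the SAP has no place to report it. The first step cannot use it because it is OLE data. The second step cannot use it because the participant is an adult.

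The former placebo participants are affected most. All their examinations up to and including Week 104 come before any venglustat, so Week 208 (or OLE early withdrawal) is their only scheduled eye examination on the drug. For adults who started on venglustat, it is the examination after the longest exposure. The protocol's history for Amendment 05 links the all-participant Week 208 examination to FDA feedback on lens monitoring at the end of treatment. Collecting it with no planned summary largely defeats that purpose.

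**Working it through.** The plan gives no figure to reproduce. The check sets the provisions side by side and then counts participants.

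1. **Which adult eye examinations are scheduled** (Protocol 1.3, notes m, n and o): screening, Weeks 26, 52, 78, 104 and 208. Weeks 130, 156 and 182 are for ages 2 to under 18 only.
2. **Which the first step can use** (SAP 3.6.3.3 and 3.8.2): screening to Week 104.
3. **Which the second step can use for adults** (SAP 3.6.3.3): none. The rule excludes every primary-population participant and every secondary-population adult.
4. **Left over for adults**: Week 208, OLE early-withdrawal examinations, and any medically necessary examination during the OLE.
5. **Against the rest of the SAP.** Section 3.6 defines second-step groups that include all primary-population participants treated in the OLE (delayed, early and all venglustat). It applies them unless a section says otherwise; 3.6.3.3 says otherwise and gives no reason drawn from the protocol schedule. Section 5.4 names ophthalmological examination among the by-visit analyses, and its Table 13 has windows up to Week 208 with no age limit.
6. **Against the amendment history.** The SAP change log for version 2.0 records an update to the OLE ophthalmology endpoint, apparently tied to Amendment 06 (the table is broken in the text available). In its visible text, Amendment 06 changed the eye-examination schedule only at Weeks 130, 156 and 182. It does not explain dropping the adult Week 208 results.

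**Counts** (planned numbers, assuming that everyone enters and completes the OLE, so upper bounds):
- Primary-population adults: 38 + 19 = 57.
- Maximum study size: 57 + 20 = 77, so primary adults are 57/77 = 74%.
- Protocol 2.3.1.1 reports 13 participants under 18 enrolled by 15 August 2022. The final number is not given. If it stayed at 13 in a full secondary population of 20, a further 20 − 13 = 7 adults would be affected: (57 + 7)/77 = 64/77 = 83%.
- Former placebo adults: up to 19, each with one scheduled eye examination on venglustat, which is not summarised.

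**Which reference point the adult summaries would use.** New-onset findings are tied to the treatment-emergent period. In the OLE this begins at OLE start (SAP 3.1), so they need no new rule. BCVA loss has no such anchor. The general baseline in SAP 3.1 precedes the first dose of the primary period, so for former placebo participants it would count the placebo period (104 weeks) as change on venglustat.

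**The case against.** The strongest reply is that the restriction is explicit and fits the protocol's view of risk. Protocol 2.3.1.1 no longer treats lens opacity as an important potential risk in adults and keeps close eye monitoring for ages 2 to under 18. Amendment 05 describes the all-participant Week 208 examination as conservative and not prompted by new safety information. The visible eye endpoints run only to Week 104, and scheduling an examination does not promise a table. The OLE endpoint rows are redacted in both documents and may themselves be limited to under 18. All of this stands as a limit on severity and confidence. It does not remove the mismatch: the SAP's account of who is monitored, and when, differs from the current protocol, and a stated rule drops safety data that the protocol requires.

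A second reply is that clinically relevant findings are caught elsewhere. That is largely right. New or worsening opacities and cataracts are adverse events of special interest (SAP Table 11). They reach the second-step adverse-event tables, which have a separate delayed-venglustat group, and the first step gives an overview of OLE adverse events up to its cut-off. Visual acuity is also part of the full physical examination at OLE visits. A reader might infer that adult lens safety in the OLE goes unreported; the documents do not support that. What is lost is the summary of examination findings, not of reported events.

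Four other inferences should be resisted:
- That four of five on-venglustat examinations are tabulated for early-start adults. The planned outputs are participant-level counts at any time, not one row per examination.
- That every former placebo participant starts venglustat the day after Week 104. Those who finished shortly before the OLE was approved could enter later (Protocol 4.1). Their Week 104 examination still precedes venglustat.
- That all delayed-start outputs need a new baseline. Only BCVA loss does.
- That the SAP simply failed to carry over Amendment 05. This is plausible but cannot be shown from the text.

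**Conclusion.** The point holds as a minor-to-moderate gap in descriptive safety reporting. On the visible text, adult OLE eye-examination results are summarised in neither step, contrary to the scope in Protocol 8.2.5 and out of line with SAP 3.6 and 5.4. It affects up to 57 primary-population adults plus any secondary-population adults. Up to 19 former placebo adults would have no summarised scheduled eye examination on venglustat. These numbers assume full entry into and completion of the OLE.

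Confidence is moderate, because the redacted OLE endpoint rows might show a deliberate age limit. Efficacy, type I error and the controlled first-step safety comparison are unaffected. The OLE summary would be uncontrolled and descriptive.

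**What to change.** In SAP 3.6.3.3:

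1. Add Week 208 and OLE early withdrawal to the list of examinations, and align the opening sentence with Protocol 8.2.5.
2. Replace the second-step sentence with:

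> In the second step, ophthalmological examinations performed in the OLE period (scheduled, early-withdrawal and unscheduled) will be summarised for all OLE participants by the Section 3.6 OLE groups; results at Weeks 130, 156 and 182 will be presented only for participants in the under-18 schedule.

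3. Leave new-onset findings on the OLE treatment-emergent period already defined in SAP 3.1.
4. For BCVA decrease only, state that the reference is the last examination before the first venglustat dose. For early-start participants this is the existing baseline. Time on drug at Week 208 then differs between groups (about 104 weeks delayed, 208 weeks early), so the separate columns should be read before the pooled one.

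If the age restriction is intended, the SAP should say so and give the reason.

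The cost is SAP wording, extra columns in tables already planned, and programming one reference rule. No new data are collected and no examination schedule changes.
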